15.3.3.2 Safety Population

The safety population is defined as all randomized subjects who received at least 1 dose of study drug (terlipressin or placebo). Treatment classification will be based on the actual treatment received.

15.3.4 Statistical Analyses

All statistical analyses will be performed and summary tables and data listings will be prepared using SAS® software version 9.2 or higher. All statistical tests will be 2-sided with a final significance level of 0.05, unless stated otherwise. When the assumptions for the planned testing methods do not hold, transformations or nonparametric methods may be employed.

15.3.5 Demographic and Baseline Characteristics

All variables concerning demographic and baseline characteristics will be summarized by treatment group and overall to describe the study population. Continuous variables will be summarized by N, mean, standard deviation, median, minimum and maximum. Categorical variables will be summarized by frequency and percentage of subjects. The summaries will be presented for all subjects in the safety and ITT populations.

15.3.6 Efficacy Analyses

All efficacy endpoints will be analyzed primarily in the ITT population. Data from the initial treatment course will be utilized in the analyses. Any retreatment courses will be evaluated separately.

15.3.6.1 Primary Efficacy Analysis

Incidence of verified HRS reversal is defined as the percentage of subjects with 2 consecutive SCr values no more than 1.5 mg/dL at least 2 hours apart, while on treatment by Day 14 or discharge (on treatment defined as up to 24 hours after the final dose of study drug). The subject must be alive without RRT for at least 10 days after achieving verified HRS reversal. SCr values after RRT, TIPS, liver transplant, or open-label vasopressor use will be excluded from primary end point analysis. SCr values obtained after midodrine administration will be included if midodrine was started on Day 1, was administered for no more than 24 hours, and the subject was enrolled on or after 17 August 2018. SCr values will also be included if obtained after the administration of a single dose of dobutamine.

Verified HRS reversal will be summarized by treatment group and analyzed using a Z Score based on the upper alpha boundary values for the interim and final analyses. The upper alpha boundary value for the interim analysis is 2.79651. At the interim analysis, if the Z score

is greater than 2.79651 then the study will stop for early success. If the Z score is no more than 2.79651 then the study will continue to the final analysis. The final analysis will be successful if the Z score is greater than 1.97743.

Table 15–2 shows the number of subjects with HRS Type 1 reversal that will be needed to achieve success at the interim analysis if the estimate of the placebo rate is accurate (approximately 12.5%).

Table 15–2: Potential Scenarios for Success at the Interim Analysis with a Placebo Rate of Approximately 12.5%

Endpoint	Terlipressin (N = 100) n (%)	Placebo (N = 50) n (%)	Z Score
Scenario 1	34 (34.0)	6 (12.0)	2.8723
Scenario 2	36 (36.0)	7 (14.0)	2.8098

15.3.6.2 Secondary Efficacy Analyses

A Hochberg procedure for multiple testing and the alpha level corresponding to the Z score of the primary efficacy analysis will be used for testing the secondary efficacy analyses at either the interim analysis or the final analysis.

If the interim analysis for the primary endpoint is successful then the secondary efficacy analyses will be tested against a corresponding p-value of 0.005166 for a Z score of 2.79651. The p-values from the 4 secondary efficacy analyses will be ordered from largest to smallest and will be compared as in Table 15–3 below:

Table 15–3: Multiple Testing for the Interim Analysis of the Secondary Efficacy Analyses

p-value Ordering	α Comparator	If p-value less than α then:	If p-value at least α then:
Largest p- value	0.005166 = 0.005166/(4 - 4 + 1)	All 4 analyses are significant	Test the second largest p-value
Second largest p-value	0.002583 = 0.005166/(4 - 3 + 1)	The remaining 3 analyses are significant	Test the third largest p-value
Third largest p-value	0.001722 = 0.005166/(4 - 2 + 1)	The remaining 2 analyses are significant	Test the smallest p-value
Smallest p- value	0.001292 = 0.005166/(4 - 1 + 1)	This analysis is significant	No analyses are significant

If the interim analysis for the primary endpoint is not successful then the study will continue onto the final analysis. If the primary efficacy analysis is successful, then the secondary efficacy analyses will be tested against a corresponding p-value of 0.047993 for a Z score of 1.97743, as shown in Table 15–4 below:

Table 15–4: Multiple Testing for the Final Analysis of the Secondary Efficacy Analyses

p-value Ordering	α Comparator	If p-value less than α then:	If p-value $\geq \alpha$ then:
Largest p- value	0.047993 = 0.047993/(4 - 4 + 1)	All 4 analyses are significant	Test the second largest p-value
Second largest p-value	0.023997 = $0.047993/(4 - 3 + 1)$	The remaining 3 analyses are significant	Test the third largest p-value
Third largest p-value	0.015998 = 0. 047993/(4 - 2 + 1)	The remaining 2 analyses are significant	Test the smallest p-value
Smallest p- value	0.011998 = 0. 047993/(4 - 1 + 1)	This analysis is significant	No analyses are significant

[figure not shown]
The following are the secondary endpoints:

[figure not shown]
- Incidence of subjects with HRS reversal, defined as the percentage of subjects with a SCr value not more than 1.5 mg/dL, while on treatment up to 24 hours after the final dose of study drug, by Day 14 or discharge. SCr values after RRT, TIPS, liver transplant, or open-label vasopressor use will be excluded. HRS reversal will be summarized by treatment group and analyzed using the Cochran-Mantel-Haenszel (CMH) chi-square test stratified by qualifying SCr (less than 3.4 mg/dL or at least 3.4 mg/dL) and pre-enrollment LVP (at least one single event of at least 4 L or less than 4 L within 3 to 14 days prior to randomization). If the proportion of subjects with HRS reversal is small (expected cell counts less than 5), an unstratified Chi-square test will be used instead of the CMH test. If the number of events per cell is still less than 5, then a Fisher's Exact test will be used.
- Durability of HRS reversal, defined as the percentage of subjects with HRS reversal without RRT to Day 30. HRS reversal is defined as the percentage of subjects with a SCr value not more than 1.5 mg/dL while on treatment by Day 14 or discharge (SCr values after RRT, TIPS, liver transplant, or open-label vasopressor use will be excluded). RRT is defined as any procedure to replace non-endocrine kidney function and includes intermittent hemodialysis, ultrafiltration, continuous hemofiltration and hemodialysis, peritoneal dialysis and other dialysis and filtration techniques. The date RRT is instituted for the first time will be used to determine if a subject underwent

[figure not shown]
RRT by Day 30. This endpoint will be summarized by treatment group and analyzed similarly to HRS reversal.

• Incidence of HRS reversal in the SIRS subgroup, defined as the percentage of SIRS subjects with HRS reversal. HRS reversal is defined as the percentage of subjects with a SCr value not more than 1.5 mg/dL while on treatment by Day 14 or discharge (SCr values after RRT, TIPS, liver transplant, or open-label vasopressor use will be excluded). This endpoint will be summarized by treatment group and analyzed similarly to HRS reversal. The SIRS subgroup is defined as any subject with at least 2 of the following criteria: WBC less than 4,000 or greater than 12,000 cells/μL; HR greater than 90 bpm; temperature greater than 38°C or less than 36°C; respiratory rate of greater than 20/min; HCO₃ less than 21 mmol/L; the latter criterion represents an approximation of the SIRS criterion PaCO₂ of less than 32 mm Hg, derived from the observed HCO₃ in subjects with HRS in whom a PaCO₂ value was available (from the TAHRS study) and the calculated HCO₃ in subjects with decompensated liver disease and PaCO₂ of less than 32 mm Hg.

Incidence of verified HRS reversal without HRS recurrence by Day 30. HRS Type 1 recurrence is defined in Section 10.5. Incidence of verified HRS reversal, defined as the percentage of subjects with 2 consecutive SCr values no more than 1.5 mg/dL at least 2 hours apart, while on treatment up to 24 hours after the final dose of study drug, by Day 14 or discharge. Subjects must be alive without RRT for at least 10 days after achieving verified HRS reversal. SCr values after RRT, transjugular intrahepatic portosystemic shunt (TIPS), liver transplant, or open-label vasopressor use will be excluded from primary end point analysis. SCr values obtained after midodrine administration will be included if midodrine was started on Day 1, was administered for no more than 24 hours, and the subject was enrolled on or after 17 August 2018. SCr values will also be included if obtained after the administration of a single dose of dobutamine. This endpoint will be summarized by treatment group and analyzed similarly to HRS reversal.

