10.4 Treatment Discontinuation

- Treatment should be continued until 24 hours after 2 consecutive SCr values no more than 1.5 mg/dL have been obtained, OR up to a maximum of 14 days (maximum of 15 days if SCr first reaches 1.5 mg/dL on Day 14).
- If on Day 4 (after a minimum of 10 doses) SCr is at or above baseline value, study drug should be discontinued.
- Treatment must be discontinued when the subject is to undergo RRT, liver transplantation, TIPS or vasopressor therapy.
- Dosing must be permanently discontinued if an event of cardiac ischemia or mesenteric ischemia occurs.

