10.7.1.2 Prohibited or Discouraged Concomitant Medications

The following medications are prohibited or strongly discouraged during treatment with study drug (Table 10–1).

Table 10–1 Prohibited/Discouraged Concomitant Medications

Prohibited Concomitant Medications

Midodrine and other vasopressive drugs including vasopressin, dopamine, dobutamine, norepinephrine. Prostaglandin analogs (eg, misoprostol).

NSAIDs (eg, ibuprofen, naproxen, diclofenac).

Octreotide.

Discouraged Concomitant Medications

Diuretics are strongly discouraged unless medically required for fluid overload; limited use of diuretics for the management of fluid overload as per standard of care may be employed and must be documented (Section 10.3.2.1.1).

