13.2.2 Pre-Treatment Period

The pre-treatment period occurs prior to administration of study drug and includes performing baseline assessments and collection of prior medication information.

• The qualifying SCr value (SCr value at least 48 hours after both diuretic withdrawal and the beginning of albumin fluid challenge) is considered the baseline SCr and must be drawn no more than 8 hours prior to start of study drug. The qualifying SCr value must be at least 2.25 mg/dL AND at least 80% of the diagnostic (pre-fluid challenge) SCr value. No subjects should be randomized unless their SCr has been obtained within 8 hours prior to randomization and start of study drug. If there is a delay in subject randomization, then the qualifying/baseline SCr value must be redrawn so that the value is collected within 8 hours prior to randomization and start of study drug to verify that the subject still meets the inclusion criterion for baseline SCr. The qualifying serum creatinine for subjects on prior vasopressors will be taken after completion of vasopressor washout. Other baseline assessments must be performed no more than 24 hours prior to start of study drug.

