13.6 Detail of Efficacy Assessments and Procedures

Serum creatinine must be collected at baseline, once daily during treatment (see Section 13.5.1.1); and then once daily (regardless of treatment status) until Day 14 or hospital discharge, whichever occurs first. If SCr assessments are performed more than once daily as part of the subject's medical care, all values obtained each day will be recorded on the eCRF. Serum creatinine values obtained after RRT, TIPS, liver transplant, or open-label vasopressor use will be excluded from the efficacy evaluation. The qualifying serum creatinine for subjects on prior vasopressors will be taken after completion of vasopressor washout.

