13.6.1 Primary Efficacy Variable

Incidence of verified HRS reversal, defined as the percentage of subjects with 2 consecutive SCr values no more than 1.5 mg/dL at least 2 hours apart, while on treatment by Day 14 or discharge (on treatment defined as up to 24 hours after the final dose of study drug). Subjects must be alive without RRT for at least 10 days after achieving verified HRS reversal. SCr values after RRT, TIPS, liver transplant, or open-label vasopressor use will be excluded from primary endpoint analysis. SCr values obtained after midodrine administration will be included if midodrine was started on Day 1, was administered for no more than 24 hours, and the subject was enrolled on or after 17 August 2018. SCr values will also be included if obtained after the administration of a single dose of dobutamine.

[figure not shown]
SCr data for the primary end point will be collected at least daily until discharge or Day 14. The analysis will be based on ITT population. Treatment should be continued until 24 hours after a second confirmatory SCr value no more than 1.5 mg/dL has been obtained, OR up to a maximum of 14 days (maximum of 15 days if SCr first reaches 1.5 mg/dL on Day 14). The date and time of the first observed SCr value of no more than 1.5 mg/dL (HRS reversal) will be used for calculating the time window for the verifying SCr value. The next (consecutive) SCr value of no more than 1.5 mg/dL must occur during the time window in order to have a verified HRS reversal. The date RRT is instituted for the first time will be used to determine if a subject underwent RRT by Day 30.

[figure not shown]

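### The midodrine/dobutamine creatinine exception covers the primary and fourth secondary endpoints but not the first three, so a verified HRS reversal need not be an HRS reversal

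*Combined protocol and SAP*

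**What the plan says.** The primary endpoint (Synopsis, 6.1.1, 13.6.1, 15.3.6.1) excludes creatinine values obtained after RRT, TIPS, transplant or open-label vasopressor use, then adds an exception. "SCr values obtained after midodrine administration will be included if midodrine was started on Day 1, was administered for no more than 24 hours", provided the subject was enrolled on or after 17 August 2018. A second sentence covers dobutamine: "SCr values will also be included if obtained after the administration of a single dose of dobutamine". The fourth secondary, verified reversal without recurrence by Day 30, carries the same two sentences wherever it is defined (Synopsis, 6.1.2, 13.6.2, 15.3.6.2).

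The first three secondaries (HRS reversal, durability of HRS reversal, HRS reversal in the SIRS subgroup) carry only the plain exclusion, "SCr values after RRT, TIPS, liver transplant, or open-label vasopressor use will be excluded", in those same sections. Section 13.6 states the general rule without any carve-out: "Serum creatinine values obtained after RRT, TIPS, liver transplant, or open-label vasopressor use will be excluded from the efficacy evaluation".

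Four other places bear on the point.

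- Table 10–1 prohibits "Midodrine and other vasopressive drugs including vasopressin, dopamine, dobutamine, norepinephrine".
- Section 13.6.1 labels the first value at or below 1.5 mg/dL as HRS reversal and starts the verification from it: "The date and time of the first observed SCr value of no more than 1.5 mg/dL (HRS reversal) will be used" to set the window for the verifying value.
- Section 13.2.2 sets the baseline floor: "The qualifying SCr value must be at least 2.25 mg/dL AND at least 80% of the diagnostic (pre-fluid challenge) SCr value". The sample is drawn no more than 8 hours before study drug.
- Section 10.4 states: "Treatment must be discontinued when the subject is to undergo RRT, liver transplantation, TIPS or vasopressor therapy".

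**The concern.** Verified reversal is the stricter endpoint. It needs two consecutive values instead of one, plus survival without RRT for 10 days, so every verified reversal should also be an HRS reversal. Because the exception is attached only to the endpoints that use the verified definition, the same creatinine value can count for the stricter endpoint and be discarded for the looser one.

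Three of the four Hochberg-tested secondaries would then rest on different data from the primary for the same subject. Section 13.6, taken as written, also contradicts the primary endpoint's own exception. If this is left open, the choice of rule could be made after the counts are known.

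**Working it through.** **1. Does the exclusion reach these drugs?** Open-label vasopressor use is not formally defined in the visible text. Table 10–1 lists midodrine and dobutamine among vasopressive drugs, exclusion criterion 17 speaks of vasopressors other than midodrine, and no exception would be needed if the exclusion did not reach them. Where the exception is absent, the exclusion therefore applies.

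**2. One subject under the literal rules.** Take a subject enrolled after 17 August 2018 with Day 1 midodrine for no more than 24 hours, later on-treatment values of 1.4 and 1.3 mg/dL, and alive without RRT at 10 days.

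| Endpoint | Exception stated? | Values counted | Result |
|---|---|---|---|
| Primary: verified reversal | Yes | 2 | Responder |
| Secondary 1: HRS reversal | No | 0 | Not a reversal |
| Secondary 2: durability | No | 0 | Not a reversal |
| Secondary 3: SIRS subgroup (if SIRS) | No | 0 | Not a reversal |
| Secondary 4: verified, no recurrence | Yes | 2 | Responder if no recurrence |

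Section 15.3.8 allows no imputation, and the plan does not say whether such a subject is a non-responder or missing for secondaries 1–3. Either way the subject is not counted as an HRS reversal.

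**3. Who is affected?** For midodrine, an earlier qualifying value is unlikely: the drug starts on Day 1 and baseline, at most 8 hours before study drug, is at least 2.25 mg/dL. A dobutamine subject is affected only if no value at or below 1.5 mg/dL came before the dose. Secondary 3 changes only for SIRS subjects.

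**4. The plan's own figures.** Z = 1.97743 gives two-sided p = 0.047993. Dividing by 1, 2, 3 and 4 gives 0.047993, 0.023997, 0.015998 and 0.011998, as in Table 15–4. A pooled two-proportion Z reproduces Table 15–2 scenario 1 (34/100 v 6/50: 2.8723). For scenario 2 it gives 2.8088 against the stated 2.8098, which is immaterial here.

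**5. What could a few subjects change?** The group sizes of 200 and 100 come from Section 15.3.1. The responder counts are assumed, with placebo near the plan's 12.5%. The test is the unstratified pooled Z, an approximation to the planned stratified CMH test:

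Z = (pT − pC) / √[p̄(1 − p̄)(1/200 + 1/100)]

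For 50/200 v 13/100: p̄ = 63/300 = 0.21; Z = (0.25 − 0.13)/√(0.21 × 0.79 × 0.015) = 0.12/0.04989 = 2.406; p = 0.0161.

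| Starting counts (T v P) | p | After loss | p | Comparator crossed |
|---|---|---|---|---|
| 60 v 14 | 0.0024 | 59 v 14 | 0.0032 | None |
| | | 58 v 14 | 0.0041 | None |
| | | 60 v 13 | 0.0012 | None |
| 50 v 13 | 0.0161 | 49 v 13 | 0.0204 | None |
| | | 48 v 13 | 0.0256 | Rises above 0.023997 |
| | | 50 v 12 | 0.0088 | Falls below 0.015998 and 0.011998 |
| 46 v 13 | 0.0400 | 45 v 13 | 0.0495 | Rises above 0.047993 |

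A crossing changes a conclusion only if that endpoint sits at the matching rank in the step-up.

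**The case against.** The strongest reply is that the limited scope looks deliberate. The Amendment 3 summary says the sentence was added after an FDA meeting and lists nine insertion points, each at the primary endpoint or the fourth secondary. This shows that the gap is not a text-extraction fault, and it may reflect an agreed position. It gives no reason, however, for counting a value towards the stricter endpoint and not the looser one, and it leaves the conflict with Section 13.6 in place.

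A second reply concerns size, and much of it stands. Midodrine must be stopped before randomization and is prohibited on treatment, and its exception covers only late enrolees. If Section 10.4 ends treatment in such subjects, the on-treatment window closes 24 hours after the last dose and few could qualify. The terlipressin design rate is not in the public text. Solving back from 89.76% power, taking 12.5% as the placebo design rate, gives about 27% (unpooled variance) to 29% (pooled), or 55 to 59 of 200. At 55 v 13, p = 0.0047, and losing three terlipressin responders (52 v 13) gives p = 0.0100, still below the strictest comparator. The crossings shown above start from 50 or 46 terlipressin responders, below that rate.

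Third, keeping the stricter rule for secondaries 1–3 would also be coherent if it were explained. That is fair, but the plan does not explain it. Sensitivity analyses (Section 15.3.6.3) are not in the public text, so any handling there cannot be seen. It would not alter the endpoint definitions that can be read.

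**Conclusion.** The concern holds. On the current text, verified HRS reversal is not a subset of HRS reversal, and Section 13.6 conflicts with the primary endpoint's exception. The conclusion depends on reading midodrine and dobutamine as open-label vasopressor use, which Table 10–1 and the existence of the exception support.

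The reach is limited. The primary result does not change, no alpha or power figure is wrong, the number affected is not stated and is probably small, and the direction is unknown. A Hochberg step changes only under some assumed counts, and not near the back-solved design rate for losses of the size examined. The point should still be fixed, because the endpoints are alpha-controlled and the ambiguity can be removed before results are known.

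**What to change.** Before unblinding, apply one creatinine-inclusion rule to the primary and all four secondaries. Add the exception sentences to secondaries 1–3 in the Synopsis, 6.1.2, 13.6.2 and 15.3.6.2, and add to the general rule in 13.6 a cross-reference to the exceptions in 13.6.1 and 13.6.2. If the difference is intended, the plan should instead say so, give the reason, and report secondaries 1–3 both ways.

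Two related items should be settled in the same amendment. The first secondary in the Synopsis lacks the on-treatment condition found in 6.1.2, 13.6.2 and 15.3.6.2 and should match them. The exception and the discontinuation text in 10.4 must be reconciled; no clinical rule is proposed here.

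The cost is a wording amendment, with the IRB and sponsor approval that Section 18.1.1 requires. Aligning the rule needs no new data and no added analysis; reporting both ways would add one further run of each of the three endpoints.

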In the REVERSE study (196 subjects with HRS Type 1 randomized 1:1 to receive terlipressin or placebo, with concomitant albumin administration recommended in both treatment arms), there was a trend for greater HRS reversals with terlipressin treatment vs placebo (24% vs 15%, p = 0.129). For a number of reasons (for example, discharge from hospital before confirmatory laboratory values), statistical significance (20% vs 13%, not significant) was not achieved for confirmed HRS reversal (an initial reduction of SCr to no more than 1.5 mg/dL followed by a confirmatory SCr measurement of no more than 1.5 mg/dL 48 hours after the initial HRS reversal [in the case of hospital discharge or transplantation before 48 hours, the 2 confirmatory SCr values had to be at least 22 hours apart]). Although the REVERSE study did not meet the prespecified endpoint of HRS reversal, the prespecified endpoint of change in SCr from baseline to end of treatment demonstrated a greater reduction in SCr with terlipressin vs placebo (-0.6 mg/dL; p = 0.0002). This current study has been designed to address the methodological obstacles encountered in the REVERSE trial.

The open-label, active-controlled study (TAHRS) and a large body of published literature studies (including 44 published clinical investigations in over 800 terlipressin-treated subjects with HRS Type 1) have consistently demonstrated that terlipressin significantly improves renal function in subjects with HRS Type 1. In TAHRS, the incidence of HRS reversal was significantly higher in terlipressin + albumin-treated subjects compared with albumin-treated subjects (39.1% vs 8.7%; p = 0.018) and the change in SCr from baseline to the end of treatment was -0.7 mg/dL (p = 0.031). Data from the literature studies consistently showed clinically relevant improvements in renal function, as measured by reduction of SCr (eg, reversal of HRS or overall change in SCr), in 20% to 83% of subjects studied. Furthermore, the literature has been analyzed in a systematic fashion by external authors in 11 meta-analyses (7 of these meta-analyses included published data from the OT-0401 and TAHRS studies), which also confirm the efficacy of terlipressin for the treatment of HRS.

Refer to the Investigator's Brochure for further details.

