5.4.1 Primary Endpoint Rationale

HRS reversal, defined as at least 1 SCr measurement of no more than 1.5 mg/dL, has been used for decades to determine treatment response in published HRS clinical studies and is the standard endpoint utilized in the literature and in HRS treatment guidelines (Arroyo et al, 1996; Salerno et al, 2007; Angeli et al, 2015). The reversal of HRS Type 1 represents a dramatic clinical response to treatment: for the endpoint to be achieved, the rapid progression of renal failure must be arrested and normal renal function restored. The purpose of the primary end point of "verified" HRS reversal is to verify that the first SCr value of no more than 1.5 mg/dL is not a spurious laboratory value. An additional element of the primary endpoint requirement, ie, alive without RRT, has been added to demonstrate the short term durability of the primary end point on clinical outcomes. RRT is defined as any procedure to replace non-endocrine kidney function and includes intermittent hemodialysis, ultrafiltration, continuous hemofiltration and hemodialysis, peritoneal dialysis and other dialysis and filtration techniques.

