13.6.2 Secondary Efficacy Variables

- Incidence of subjects with HRS reversal, defined as the percentage of subjects with a SCr value no more than 1.5 mg/dL while on treatment by Day 14 or discharge (SCr values after RRT, TIPS, liver transplant, or open-label vasopressor use will be excluded).
- Durability of HRS reversal: the percentage of subjects with HRS reversal without RRT to Day 30. HRS reversal is defined as the percentage of subjects with a SCr value no more than 1.5 mg/dL while on treatment by Day 14 or discharge (SCr values after RRT, TIPS, liver transplant, or open-label vasopressor use will be excluded). RRT is defined as any procedure to replace non-endocrine kidney function and includes intermittent hemodialysis, ultrafiltration, continuous hemofiltration and hemodialysis, peritoneal dialysis and other dialysis and filtration techniques. The date RRT is instituted for the first time will be used to determine if a subject underwent RRT by Day 30.
- Incidence of HRS reversal in the SIRS subgroup: the percentage of SIRS subjects with HRS reversal. HRS reversal is defined as the percentage of subjects with a SCr value no more than 1.5 mg/dL while on treatment by Day 14 or discharge (SCr values after RRT, TIPS, liver transplant, or open-label vasopressor use will be excluded). The SIRS subgroup is defined as any subject with at least 2 of the following criteria: WBC less than 4,000 or greater than 12,000 cells/μL; heart rate greater than 90 bpm; temperature greater than 38°C or less than 36°C; respiratory rate greater than 20/min; HCO₃ less than 21 mmol/L; the latter criterion represents an approximation of the SIRS criterion PaCO₂ of less than 32 mm Hg, derived from the observed HCO₃ in subjects with HRS in whom a PaCO₂ value was available (from the TAHRS study) and the calculated HCO₃ in subjects with decompensated liver disease and PaCO₂ of less than 32 mm Hg.

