15.3 Statistical Methodology

15.3.1 Sample Size Calculation

NOTE: Based on REVERSE, subjects without a known event of pre-enrollment LVP at least 4 L within 2 days of randomization and OT-0401 subjects with baseline SCr no more than 7 mg/dL. SCr values were included while the subjects were on treatment, up to 24 hours after the final dose of study drug. SCr values were excluded after RRT and transplant. If a subject died within 10 days after the reversal, then the subject did not have a reversal. If a subject has an RRT by the 30-day follow-up visit, then the subject did not have a reversal. Three REVERSE terlipressin subjects who achieved a reversal after the 24 hour window were counted as reversals because they would have continued on study drug based on the CONFIRM trial design through the reversal.

With a 2:1 randomization of terlipressin to placebo and an interim analysis after 50% of the subjects have completed Day 14 or Discharge, 300 subjects will provide 89.76% power to detect a statistically significant difference between the groups, 200 subjects in the terlipressin group and 100 subjects in the placebo group.

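### The Day 30 durability endpoint has no survival condition, so read literally a reverser who dies before Day 30 without RRT meets it

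*Combined protocol and SAP*

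**What the plan says.** The durability endpoint is stated in the Synopsis and in Sections 6.1.2, 13.6.2 and 15.3.6.2. Section 15.3.6.2 has: "Durability of HRS reversal, defined as the percentage of subjects with HRS reversal without RRT to Day 30". In each place the reversal component is a single on-treatment SCr of at most 1.5 mg/dL, not verified reversal. Sections 6.1.2, 13.6.2 and 15.3.6.2 add one operational rule: "The date RRT is instituted for the first time will be used to determine if a subject underwent RRT by Day 30". The Synopsis does not carry that sentence.

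Elsewhere the plan writes survival in:

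- Primary endpoint (15.3.6.1): "The subject must be alive without RRT for at least 10 days after achieving verified HRS reversal".
- Fourth secondary, verified reversal without recurrence (15.3.6.2): "Subjects must be alive without RRT for at least 10 days after achieving verified HRS reversal".
- Rationale for the primary endpoint (5.4.1): "alive without RRT, has been added to demonstrate the short term durability of the primary end point on clinical outcomes".
- Scoring of the earlier-study data used for planning (15.3.1): "If a subject died within 10 days after the reversal, then the subject did not have a reversal".

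Durability is tested under a Hochberg procedure: "The p-values from the 4 secondary efficacy analyses will be ordered from largest to smallest". This happens only if the primary analysis succeeds. Efficacy is analysed primarily in all randomized subjects (15.3.3.1, 15.3.6), and missing data are not imputed unless otherwise stated (15.3.8).

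**The concern.** Death prevents later RRT. An endpoint that looks only for RRT therefore cannot tell a subject whose kidney recovery lasted to Day 30 from one who died first. A subject with a qualifying SCr on Day 5 who dies on Day 7 without RRT has a reversal and no RRT date, and so satisfies the durability wording. The same subject fails the primary endpoint. The 10-day survival element does not carry over, because it belongs to verified reversal and durability is not built on verified reversal.

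At stake is the meaning of a percentage that would be reported, and possibly claimed under alpha control, as durable reversal. If RRT-free deaths among reversers differ between arms, the treatment comparison is affected too.

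**Working it through.** **Reading the definition.** Three questions settle what the text does with a reverser who dies before Day 30 without RRT.

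1. Does any statement of the endpoint say alive? No, in none of the four places.
2. Does any rule turn death into failure? None in the public text. Section 15.3.8 sets no imputation, and the rule in 15.3.1 describes planning data from earlier studies.
3. What decides the Day 30 part? Only the date of first RRT, where a rule is given at all.

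So the literal result is a success.

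**Inputs for an illustration.** 200 terlipressin and 100 placebo subjects (15.3.1). Reversal rates from Section 5.3.2: OT-0401, 34% v 13%; for REVERSE, "there was a trend for greater HRS reversals with terlipressin treatment vs placebo (24% vs 15%, p = 0.129". Final-analysis Hochberg levels from Table 15-4: 0.047993, 0.023997, 0.015998 (Z = 1.977, 2.257, 2.409). Assumptions: no RRT among reversers, and every share of RRT-free death, because the documents give none.

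**Formula.** Z = (a/n − b/m) / √[p(1 − p)(1/n + 1/m)], with p = (a + b)/(n + m). This approximates the stratified CMH test named in the plan. Check against Table 15-2: 34/100 v 6/50 gives 2.8723, as printed; 36/100 v 7/50 gives 2.8088 (printed 2.8098).

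Successes under an alive-and-RRT-free definition = reversers × (1 − RRT-free death share).

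**OT-0401 rates (68 v 13 reversers)**

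| Assumed death share, terlipressin / placebo | Successes | Difference (points) | Z |
|---|---|---|---|
| as written | 68 v 13 | 21.0 | 3.86 |
| 10% / 10% | 61.2 v 11.7 | 18.9 | 3.60 |
| 20% / 20% | 54.4 v 10.4 | 16.8 | 3.33 |
| 30% / 30% | 47.6 v 9.1 | 14.7 | 3.07 |
| 40% / 40% | 40.8 v 7.8 | 12.6 | 2.79 |
| 30% / 10% | 47.6 v 11.7 | 12.1 | 2.48 |
| 10% / 30% | 61.2 v 9.1 | 21.5 | 4.14 |

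With equal shares of 10% to 40%, about 7 to 27 terlipressin deaths (68 × 0.10 to 68 × 0.40) and 1 to 5 placebo deaths (13 × 0.10 to 13 × 0.40) would be counted as durable.

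**When would a conclusion change?** HRS reversal itself stays at Z = 3.86. When survival-conditioned durability has a larger p-value than that, the strictest step it can face is 0.015998. Fix the placebo share at 10% (11.7 successes) and count whole terlipressin deaths among 68 reversers:

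- 21 deaths: 47 v 11.7, Z = 2.43; 22 deaths: 46 v 11.7, Z = 2.34. Missing 2.409 takes 22.
- 26 deaths: 42 v 11.7, Z = 1.981; 27 deaths: 41 v 11.7, Z = 1.888. Missing 1.97743 takes 27.

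**REVERSE rates (48 v 15 reversers).** As written Z = 1.80 (p = 0.071), not significant. Equal shares of 10% to 40% give 1.69 to 1.33. Shares of 30% v 10% give 33.6 v 13.5, Z = 0.74. Shares of 10% v 30% give 43.2 v 10.5, Z = 2.36 (p = 0.0181), which meets 0.047993 and 0.023997 but not 0.015998. Here the current wording could hide a difference rather than create one.

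**The case against.** **No sentence says that RRT-free death is a success.** That is correct. A reader might infer that the plan deliberately credits deaths; the documents do not say so. One could also read the phrase about Day 30 as requiring observation to Day 30. But the only rule given is the RRT date. If survival was meant, the handling of death is unwritten and still has to be supplied.

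**Section 5.4.1 is about the primary endpoint, and 15.3.1 about planning data.** Also correct. Neither governs this secondary endpoint, so a reader who infers that the plan breaks its own rule goes too far. What stands is a contrast: survival is written in where short-term durability of the primary endpoint is to be shown, and is absent from the endpoint named durability.

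**An RRT-only endpoint may be intended.** Freedom from RRT is a coherent kidney outcome. Amendment 1, which answered the Special Protocol Assessment letter, spelled out the reversal and RRT definitions in this bullet without adding survival. This bears on the choice of remedy, but it does not change what the percentage counts.

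**The primary endpoint is a gate.** It protects in part. Suppose all reversers were verified and all deaths fell within 10 days. In the 27-death case the primary would have the same Z of 1.888 and durability would not be tested. In the 22-death case the primary Z of 2.34 would pass. Later deaths, and deaths in reversers who were never verified, are outside the gate's reach.

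**Unseen text may help.** Sections 6.1.3, 6.1.4 and 15.3.6.3 are not in the public text. The summary of changes links 15.3.6.3 to the recurrence assumption. A supportive analysis handling death may exist there, but it would not alter the tested definition.

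**Conclusion.** The point holds as a defect in the definition of one gated secondary endpoint. As written, the durability percentage can include subjects who died before Day 30 without RRT.

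The tempting stronger conclusion is that the wording inflates the terlipressin effect or produces a false positive. The documents do not support that. They give no death rates among reversers, and the effect can go either way. At OT-0401 rates, equal shares of 10% to 40% leave the result significant. A lost step needs a marked imbalance: 22 of 68 terlipressin reversers against an assumed 10% on placebo for the 0.015998 step, 27 of 68 for 1.97743. At REVERSE rates the wording as it stands gives no significant result.

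These figures rest on borrowed reversal rates, assumed death shares, no RRT among reversers and an unstratified Z. It should be fixed. Confidence is medium, because an RRT-only endpoint may have been agreed.

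**What to change.** Before unblinding, define durability as HRS reversal and alive without RRT to Day 30, judged by the dates of death and first RRT. Make the wording identical in the Synopsis and Sections 6.1.2, 13.6.2 and 15.3.6.2. Add a rule for subjects whose survival to Day 30 is unknown. Keep the RRT-only version as a supportive analysis.

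If the RRT-only definition must stay as the tested endpoint, then:

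- pre-specify the alive-and-RRT-free version as supportive;
- state that death before Day 30 without RRT counts as success in the tested version;
- tabulate RRT-free deaths among reversers by arm.

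No new data are needed: Table 13-1 records RRT and mortality through follow-up, and Section 14.2 collects deaths to 90 days after first dose. The cost is an amendment, regulator agreement if the Special Protocol Assessment requires it, and somewhat lower durability rates. The primary endpoint, sample size and power do not change.
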